6.7. Adverse events

Pertinent to safety assessment, the status of adverse events after the commencement of Genotropin therapy should be verified and the following information should be recorded. Adverse events should be verified in principle until the assessment period for each booklet is completed. Upon occurrence of any adverse event, the investigator shall provide appropriate intervention, promptly report to Sponsor in accordance with "Adverse event reporting" (Attachment 1), and follow up on the progress and outcome in principle until the symptoms disappear. Also, the investigator shall quickly notify Sponsor, "if a patient or the patient's partner conceives, or it has been found out that a patient or the patient's partner has conceived, whether adverse event has occurred or not," "if a serious adverse event occurred," and if any follow-up information thereto related has been obtained. Refer to "Adverse event reporting" (Attachment 1) for the details of procedures.

Furthermore, any occurrence of intrauterine exposure, or a serious adverse drug reaction or an adverse reaction not described in the package insert should be separately investigated as determined necessary by Sponsor.

- [1] Presence/absence of adverse event
- [2] Name of adverse event
- [3] Date of onset
- [4] Intervention
- [5] Seriousness
- [6] Outcome
- [7] Causal relation with Genotropin

[The following variables should be recorded if the adverse event is associated with abnormal test results, e.g., clinical laboratory]

- [8] Laboratory parameter

Ver.2

[9] Site reference

[10] Unit

[11] Date of measurement

[12] Result

Note: An adverse event is any untoward medical occurrence in a subject following Genotropin dose (including clinically significant change in laboratory test results); the event needs not necessarily to have a causal relationship with the treatment. A serious adverse event is any untoward medical occurrence that; Results in death; Is life-threatening (immediate risk of death), Requires inpatient hospitalization or prolongation of existing hospitalization; Results in persistent or significant disability/incapacity; Results in congenital anomaly/birth defect; or otherwise may result in medically important event or disorder.

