6.8. Height follow-up after completion or discontinuation of Genotropin therapy

"Height Follow-up Form" will be used to collect data concerning body height in patients completing or discontinuing Genotropin therapy, and meeting the following criteria.

- Patients not switching to other drug product
- Patients not reaching adult height (final height)

[1] Date on which height follow-up is completed

[2] Height (to the first decimal place), and weight (to the first decimal place)

[3] Bone age

[4] Pubescence

[5] Future treatment strategy

Note: Any occurrence of adverse event during the height follow-up period should be separately investigated in details as determined necessary by Sponsor.

7. Analysis plan

Statistical analysis on safety and efficacy shall be performed; the results of which shall be posted in scientific journal, and reported at academic conferences and through research activities. In no event shall the investigator inquire Sponsor to perform statistical analysis for this investigation without confirming with Japan Genotropin Advisory Board in advance.

8. Discontinuation

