The following treatment status of Genotropin will be summarized in the safety analysis set.

- Dose at start (continuous variable) [less than 0.23 mg/kg/week, 0.23 mg/kg/week or higher and less than 0.35 mg/kg/week, 0.35 mg/kg/week or higher and less than 0.47 mg/kg/week, 0.47 mg/kg/week or higher]: Dose per week/kg body weight described at the starting date of the first treatment.
- Duration of treatment (continuous variable) [less than 1 year, 1 year or longer and less than 2 years, 2 years or longer and less than 3 years,---, N years or longer and less than N + 1 year]: (ending date of the last treatment - starting date of the first treatment + 1) /365.25.

The Duration of treatment is defined as the period from the first treatment day to the day of the last treatment confirmed in this investigation, including washout period.

To confirm the dose modification, the dose per week/kg, change in the dose from the start of Genotropin, and change in the dose from the previous year will be summarized at the start of Genotropin and once a year thereafter. The body weight value measured on the earliest date in each period will be used to calculate the dose per week/kg. The dose per week/kg will be considered as missing when there is no body weight measurement during the period.

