8.2.3. Safety Analysis

8.2.3.1. Adverse Drug Reactions

- **All adverse drug reactions**

The number and proportion of patients who developed an adverse drug reaction will be summarized by SOC and PT.

- **Serious adverse drug reactions**

The number and proportion of patients who developed a serious adverse drug reaction will be summarized by SOC and PT.

- **Details on adverse drug reaction**

The number and proportion of patients who developed an adverse drug reaction will be summarized by SOC and PT for each of the following items.

- Seriousness [serious, non-serious].
- Known/unknown [known, unknown].

- Measures taken [permanently discontinued, temporarily discontinued, dose reduced, dose increased, no dose change].
- Outcome [not recovered, recovered with sequelae, resolving, disappeared/resolved, unknown].

When the same patient experiences the same adverse drug reaction (with the same PT) more than once, the adverse drug reaction will be handled as follows in summarizing the number of patients with the adverse drug reaction.

- Seriousness: The adverse drug reaction will be handled as serious when it develops as both serious and non-serious events.
 - Known/unknown: The adverse drug reaction will be handled as unknown when it develops as both known and unknown events.
 - Number of days before onset: The number of days before the adverse drug reaction developed for the first time.
 - Measures taken: When more than one measure has been taken, one of them will be employed with the order of preference of permanently discontinued, temporarily discontinued, dose reduced, and others (no measure/dose increased).
 - Outcome: The outcome of the event that developed last will be used.
- **Timing for development of adverse drug reaction**

The number of patients who develop an adverse drug reaction for the first time in less than 1 year after the start of treatment will be summarized by SOC and PT for patients who receive Genotropin for less than 1 year. Similarly, the number of patients who develop an adverse drug reaction for the first time during the period of 1 year or longer and less than 2 years after the start of treatment will be summarized by SOC and PT for patients who receive Genotropin for 1 year or longer and less than 2 years. The same will be repeated to summarize it for the period of 2 years or longer and less than 3 years and so on (N years or longer and less than N + 1 years).

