The number of patients will be summarized cumulatively. For example, patients for whom the duration of treatment is 2 years or longer and less than 3 years will be included in patients for whom the duration of treatment is less than 1 year and those for whom the duration of treatment is 1 year or longer and less than 2 years.

- **Development status of adverse drug reaction by inclusion in safety analysis set**

A list of adverse drug reactions in patients excluded from the safety analysis set will be prepared for the patients for whom the report form is collected. Furthermore, the number of patients who develop an adverse drug reaction will be summarized by SOC and PT.

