8.2.3.2. Adverse Event

- **All adverse events**

The number and proportion of patients who develop an adverse event will be summarized by SOC and PT.

- **Adverse events by seriousness**

The number and proportion of patients who developed serious adverse events will be summarized by SOC and PT. The number and proportion of patients who develop a non-serious adverse event will be summarized in the same manner.

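### The reaction-timing table drops first reactions that start in a later treatment year than the one in which treatment ended and mixes other post-treatment reactions with on-treatment ones; the Height Follow-up Form does not routinely ask about adverse events.

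*SAP*

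**What the plan says.** **Timing table (SAP 8.2.3.1, timing for development of adverse drug reaction).** The first row counts reactions that occur "for the first time in less than 1 year after the start of treatment", among children treated for less than one year. The second row counts onsets in the second year "for patients who receive Genotropin for 1 year or longer and less than 2 years", and so on. The SAP adds: "The number of patients will be summarized cumulatively". Its example places a child treated for two to three years in the two earlier rows as well.

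**Treatment duration (SAP 8.2.2).** It runs from the first treatment day "to the day of the last treatment confirmed in this investigation, including washout period". Gaps within treatment count; time after the last dose does not.

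**Overall tables (SAP 8.2.3.1 and 8.2.3.2).** "The number and proportion of patients who developed an adverse drug reaction will be summarized by SOC and PT", and for events of any cause, "The number and proportion of patients who develop an adverse event will be summarized by SOC and PT". Neither limits onset relative to the end of treatment. The lists in SAP section 9 have no such limit either.

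**Collection (protocol sections 6, 6.7 and 6.8).** The assessment schedule marks adverse events for Booklet 01 and Booklet 02, but not for the Height Follow-up Form. The items in section 6.8 are the follow-up completion date, height and weight, bone age, pubescence and future treatment strategy. Two sentences bear on adverse events: "Adverse events should be verified in principle until the assessment period for each booklet is completed" (6.7) and "Any occurrence of adverse event during the height follow-up period should be separately investigated in details as determined necessary by Sponsor" (6.8).

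**The concern.** The stated objective covers long-term safety, and the timing table is where a reader would look for late-onset reactions. Each of its rows sets two conditions: onset falls in that year, and treatment reached that year. A reaction after stopping may meet the first and fail the second, and then it is absent without any note. A reaction after stopping that meets both is shown alongside on-treatment reactions. The table is thus neither a clean on-treatment table nor a complete table of onset times. Children who stopped because of an adverse event are among those affected.

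On collection, height follow-up can run to adult height or the end of the investigation (protocol 5.4.3), yet its form does not ask whether an adverse event occurred. The section 6.8 note deals with an event once it is known; it does not prompt anyone to ask.

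**Working it through.** The plan states no figure to reproduce here, so the check applies the rule literally.

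**Inputs.** Let d be the treatment duration in years (SAP 8.2.2) and t the onset of the first reaction in years from the start of treatment (SAP 8.2.3.1). Row k covers onsets from k to under k+1 years. With the cumulative rule it contains children with d of at least k. A reaction therefore has a row only if floor(d) ≥ floor(t).

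**Example children, all with onset after stopping (t > d).**

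| d | t | t − d | floor(d) | floor(t) | In table? |
|---|---|---|---|---|---|
| 0.4 | 0.9 | 0.5 | 0 | 0 | yes |
| 0.9 | 1.2 | 0.3 | 0 | 1 | no |
| 1.2 | 1.9 | 0.7 | 1 | 1 | yes |
| 1.9 | 2.1 | 0.2 | 1 | 2 | no |
| 1.5 | 4.0 | 2.5 | 1 | 4 | no |
| 3.0 | 3.5 | 0.5 | 3 | 3 | yes |

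An onset 0.7 years after stopping is counted and one 0.2 years after stopping is not. What decides is whether a treatment anniversary falls between the stop and the onset. On-treatment reactions are never lost: t ≤ d implies floor(t) ≤ floor(d).

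**Illustrative share without a row.** The following is an assumption, not taken from the documents. Let the time from stopping to the next anniversary be uniform on 0 to 1 year, and the delay from stopping to onset uniform on 0 to F years. A reaction has no row if the delay exceeds the time to the anniversary.

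- For F ≤ 1: share = F/2. F = 0.25 gives 0.125; F = 1 gives 0.50.
- For F ≥ 1: share = 1 − 1/(2F). F = 3 gives 1 − 1/6 = 0.83; F = 5 gives 1 − 1/10 = 0.90.

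The answer depends almost wholly on F, the window over which post-treatment reactions come to notice. The documents do not fix it. Booklet periods run to the fiscal year end (protocol 5.4.1 and 5.4.2), but height follow-up begins at completion or discontinuation (5.4.3), so it is unclear which form covers the rest of the year in which treatment stops. With no reaction rate given either, these shares cannot be turned into a number of children.

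**Collection.** The schedule and the section 6.8 item list agree: the Height Follow-up Form has no adverse event item. The form goes only to children who stopped, did not switch product and have not reached adult height (5.5.3 and 6.8). Children who switched or reached adult height get no form.

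**The case against.** The strongest reply is that little is lost. The all-reactions, serious-reaction, detail and adverse event tables and the listings carry no duration limit, so a reported post-treatment reaction is missing from one descriptive sub-table only. Onset dates are collected, and SAP 8.2.3.1 has a handling rule for days to onset that does not depend on duration. Limiting each row to children treated that long can be read as deliberate matching to exposure, nothing requires the rows to add up to the overall count, and the analysis is declared non-confirmatory (SAP 4.1).

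The reply on collection is that protocol 6.7 requires prompt reporting, follow-up in principle until symptoms disappear, and quick notification of serious events, with no end date in the text. The 6.8 note may leave to the sponsor only the depth of inquiry, not whether an event is reported. Details are deferred to Attachment 1, whose content is not in the text available, so its reporting window could not be checked.

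Most of this stands, and it limits the point. It does not rescue the timing rule: a table matched to exposure would exclude every post-treatment onset, whereas this one keeps some and drops others according to the anniversary. Nor does a duty to report known events replace a routine question, least of all for non-serious events.

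**Conclusion.** The point holds in two limited parts.

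1. The timing table omits first reactions that start in a later yearly interval than the one in which treatment ended, and merges other post-treatment reactions with on-treatment ones. Inclusion depends on where in the treatment year the child stopped, and the table can differ from the all-reactions table without explanation. This follows from the SAP's wording alone.
2. Adverse events are not routinely asked about on the Height Follow-up Form, so non-serious post-treatment events in particular are not systematically sought. Serious-event notification may still capture some.

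A reader might infer that reactions after treatment have no place in the timing table at all. The SAP does not support that: those in the same yearly interval as the stop are counted. A reader might also infer that the safety record ends when treatment stops. The documents do not support that either, given the unrestricted tables and the reporting duties in protocol 6.7.

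The size cannot be stated. The 12.5% to 90% range is an illustration under the uniform assumptions, as a share of an unknown count. Overall reaction counts are unaffected by the timing rule, but it should be corrected before the final analysis.

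**What to change.** **SAP 8.2.3.1.** Place a first reaction with onset on or before the last Genotropin date in the yearly row of its onset, among children treated into that interval. Put a first reaction with onset after the last Genotropin date in one separate post-treatment row, with children who stopped as denominator. The yearly rows must exclude post-treatment onsets; otherwise the new row counts them twice. Each first reaction with a known onset date then appears once, and the rows reconcile with the all-reactions table when first is defined at the same SOC or PT level. The cost is a short SAP revision and one extra row, using onset and treatment dates already collected.

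**Protocol 6.8 and the Height Follow-up Form.** Add an adverse event yes/no item and, if yes, name, onset date, seriousness and causality. Data after treatment may already be collected by telephone. The cost is a protocol and form revision and some extra event reports to process. It helps only contacts still to come, and children who switched product or reached adult height stay uncovered because they receive no such form; the report should say so.

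The SAP change can be made without the form change.

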8.2.3.2. Adverse Event

- **All adverse events**

The number and proportion of patients who develop an adverse event will be summarized by SOC and PT.

- **Adverse events by seriousness**

The number and proportion of patients who developed serious adverse events will be summarized by SOC and PT. The number and proportion of patients who develop a non-serious adverse event will be summarized in the same manner.

8.2.3.3. Other Endpoints

- **Laboratory test parameters**

The summary statistics of measured values of HbA1c at each evaluation point and change from the start of Genotropin will be calculated. The 95% confidence interval of the mean of the change will be calculated. The evaluation points are according to [Appendix A1.3](#) Definition of timing for visit 3.

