6.2. Family history and patient characteristics

(1) The following information obtained at the commencement of Genotropin therapy will be recorded:

- [1] Height of parents (to the first decimal place)
- [2] Mother's birth history (the first childbirth / multipara)
- [3] Presence/absence of GHD family history
- [4] Twin/multiplets
- [5] Childbirth procedures
- [6] Fetus week number
- [7] Apgar score
- [8] Birth height (to the first decimal place)
- [9] Birth weight (to the first decimal place)
- [10] Birth head circumference (to the first decimal place)
- [11] Body height at 1 year prior to the commencement of treatment (to the first decimal place), and the date of measurement
- [12] GH tolerance test
- [13] Clinical history (past history and concurrent disease)
 - Silver-Russell syndrome
 - Name(s) of disease/syndrome
 - Past or current regarding the following clinical history
Chronic disease (including allergy), disease requiring medical treatment, disease/disorder accompanied by surgery, hospitalization, and/or subsequent complications, or any other

Ver.2

disease/syndrome determined problematic; of which, those occurred prior to the commencement of Genotropin therapy will be considered as "Past history", and those concurrent at the commencement of Genotropin therapy will be considered as "Concurrent disease".

[14] Prior medications

Presence/absence of growth hormone therapy intended for the treatment of SGA (small-for-gestational age) dwarfism without epiphyseal closure used until the day before the commencement of Genotropin therapy

(2) The following status will be recorded until the completion of assessment period for each booklet:

[1] Presence/absence of pregnancy, and the actual or expected date of birth [women only]

[2] Verification of revisits since the commencement of treatment (this checkmark is not required if not applicable)

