5.4. Subsets

The following patient characteristics will be analyzed for efficacy by subsets.

- Age [less than 5 years, 5 years or older and less than 7 years, 7 years or older].
- Mother's birth history [the first childbirth / multipara].
- Presence/absence of GHD family history.
- Twin/multiplets.
- Fetus week number [less than 33 weeks, 33 weeks or older and less than 37 weeks, 37 weeks or older].

- Silver-Russell syndrome [yes, no].
- Period from the first date of treatment with growth hormone products including Genotropin to the pubescence [less than 2 years, 2 years or longer].

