11. APPENDIXES

11.1. Appendix 1: Details of Data Extraction

A1.1 DEFINITION OF TIMING FOR VISIT 1

Timing for visit	Endpoint	Definition [allowable range]
3 years	Height Height SDS Body weight SDS BMI SDS IGF-I SDS	3 years and 0 month to 3 years and 11 months
4 years	Height Height SDS Body weight SDS BMI SDS IGF-I SDS	4 years and 0 month to 4 years and 11 months
N years	Height Height SDS Body weight SDS BMI SDS IGF-I SDS	N years and 0 month to N years and 11 months

The measured value on the latest date will be used when the same patient receives more than one measurement during the same visit.

A1.2 DEFINITION OF TIMING FOR VISIT 2

Timing for visit	Endpoint	Definition [allowable range]
Start of Genotropin therapy	Height SDS Body weight SDS BMI SDS IGF-I SDS	90 days before the first date of treatment (the start date of treatment) to the start date of treatment for this investigation
Pubescence	Height SDS Body weight SDS BMI SDS IGF-I SDS	The date evaluated as the pubescence +90 days
At reaching adult height (near final height)	Height SDS Body weight SDS BMI SDS IGF-I SDS	The date evaluated to reach adult height (near final height) +90 days

The measured value on the earliest date will be used when the same patient receives more than one measurement during the same visit.

In this regard, all the data measured after reaching adult height (near final height) will be used if plots are prepared.

A1.3 DEFINITION OF TIMING FOR VISIT 3

Timing for visit	Endpoint	Definition [allowable range]
Start of Genotropin therapy	Laboratory test parameters Height SDS Height velocity Height velocity SDS Body weight SDS BMI SDS IGF-I SDS	90 days before the first date of treatment (the start date of treatment) to the start date of treatment for this investigation
1 year later	Laboratory test parameters Height SDS Height velocity Height velocity SDS Body weight SDS BMI SDS IGF-I SDS	365 ±90 days after the start of treatment
2 years later	Laboratory test parameters Height SDS Height velocity Height velocity SDS Body weight SDS BMI SDS IGF-I SDS	730 ±90 days after the start of treatment
N years later	Laboratory test parameters Height SDS Height velocity Height velocity SDS Body weight SDS BMI SDS IGF-I SDS	365 × N ±90 days after the start of treatment
Completion of Genotropin therapy	Laboratory test parameters Height SDS Height velocity Height velocity SDS Body weight SDS BMI SDS IGF-I SDS	Final date of treatment for this investigation (completion date of treatment) ±90 days

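### HbA1c change from the start of Genotropin pools growth-hormone-naive children with children previously given another growth hormone, and no readable safety table separates them

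*SAP*

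**What the plan says.** **HbA1c.** SAP 8.2.3.3 reads: "The summary statistics of measured values of HbA1c at each evaluation point and change from the start of Genotropin will be calculated". A 95% confidence interval for the mean change follows. The baseline window in SAP Appendix A1.3 is "90 days before the first date of treatment (the start date of treatment) to the start date of treatment for this investigation", with no condition that the child be free of growth hormone. HbA1c is the only laboratory parameter with a readable summary in the SAP's safety section.

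**Prior growth hormone.** Protocol 6.2 item [14] records "Presence/absence of growth hormone therapy intended for the treatment of SGA" dwarfism, covering use up to the day before Genotropin begins. Protocol 5.3.1 and 6.1 collect the date of first growth hormone separately from the Genotropin start date. Neither the enrollment criteria (protocol section 2) nor the safety-set exclusions (SAP 5.1) bar prior use.

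**Reaction timing.** SAP 8.2.3.1 asks for "The number of patients who develop an adverse drug reaction for the first time in less than 1 year after the start of treatment", then repeats this for later years in bands of time on Genotropin. SAP 8.2.2 defines duration, under Genotropin treatment status, as the "period from the first treatment day to the day of the last treatment confirmed in this investigation". Protocol 6.7 says that "the status of adverse events after the commencement of Genotropin therapy should be verified", so events on an earlier product are not collected.

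**Use of prior growth hormone in the analysis.** The objective (protocol section 1, SAP 2.2) lists earlier growth hormone treatment among the factors to relate to response. SAP 5.4 opens: "The following patient characteristics will be analyzed for efficacy by subsets". Its list has no naive versus previously treated split. SAP 6.4 names no covariates, and SAP 8.2.2 only describes pretreatment drugs.

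**The concern.** A child switched directly from another product has a baseline measured on growth hormone. Any HbA1c shift that occurred on the earlier product is already in that baseline and drops out of the change score. Averaging such children with naive children gives a mean that describes neither group.

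Safety results from this investigation go to regulators on request and are meant for publication. A reader of the pooled mean and interval would naturally take them as the metabolic effect of starting growth hormone. The table could not show whether that reading is sound, because it does not say how many children had a prior product or how they differed. The reaction-timing table has the same gap: its first-year row combines children in their first year of any growth hormone with children who may be in a later year.

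**Working it through.** The plan gives no HbA1c effect, SD, reaction rate or share of previously treated children. The target of 400 has no derivation. There is therefore no planned figure to reproduce, and the arithmetic below is an illustration.

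**Step 1. Formula.** Let d be the mean HbA1c change in naive children at a given visit, s the share of analysed children with prior growth hormone, and r×d the mean further change in that share.

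Pooled mean = (1-s)×d + s×r×d = d × [(1-s) + s×r].

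The shift from the naive value is d×s×(1-r). For 0 ≤ r < 1 and s > 0 the pooled mean lies closer to zero than d, whichever sign d has.

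**Step 2. Pooled change as a share of the naive change (s and r assumed).**

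| s | r = 0 | r = 0.5 | r = 1 |
|---|---|---|---|
| 0 | 100% | 100% | 100% |
| 5% | 95% | 97.5% | 100% |
| 10% | 90% | 95% | 100% |
| 20% | 80% | 90% | 100% |
| 30% | 70% | 85% | 100% |
| 50% | 50% | 75% | 100% |

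For example, at s = 20% and r = 0.5: 0.8 + 0.2×0.5 = 0.9.

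**Step 3. Size against the interval.** Assume d = 0.2 percentage points and SD of change 0.3.

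- Half-width at 400 children: 1.96×0.3/√400 = 0.029. At 200 children: 1.96×0.3/√200 = 0.042.
- Shift at s = 10%: 0.2×0.1×1 = 0.02 (r = 0) or 0.2×0.1×0.5 = 0.01 (r = 0.5).
- Shift at s = 20%: 0.04 (r = 0) or 0.02 (r = 0.5).

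At s = 20% the shift is about as large as the half-width when r = 0, and below it when r = 0.5. At s = 10% it is below it in both cases.

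**Step 4. Reaction timing.** The timing paragraph specifies numbers of patients, whereas the all-reaction and serious-reaction tables specify number and proportion. For a count, total = naive cases + previously treated cases, so adding previously treated children cannot lower the number of naive cases shown. The formula in Step 1 does not apply to this table as written. The table's limitation is that the two groups cannot be told apart.

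**Step 5. Which clock.** SAP 8.2.3.1 says start of treatment without naming the product. The bands are defined by time on Genotropin, duration is defined under Genotropin treatment status, and events are collected from the Genotropin start. SAP 5.4, where it means any growth hormone, says so. The timing clock is therefore read here as a Genotropin clock.

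**The case against.** **The time origin is defensible.** This is post-marketing surveillance of Genotropin. SAP 6.1 defines adverse drug reactions by their relation to Genotropin, so change since starting Genotropin is the product's own question. That stands, and it is why the pooled summary should stay. The change in naive children is a second question, which the objective also raises.

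**The HbA1c change is not the only metabolic information.** Measured values are summarised at each visit, laboratory parameters are listed (SAP section 9), and clinically significant laboratory changes count as adverse events. This is true, but none of these readable outputs is split by prior growth hormone.

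**The share may be small.** The entry limits on height and pre-treatment height velocity may screen out some previously treated children, and enrollment violators leave the safety set. This may limit s, but it does not bar prior use. Children carried over from the earlier Genotropin investigation are not a problem in themselves, because SAP 2.1 brings their earlier data into the analysis.

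**Not every previously treated child has an on-treatment baseline.** Item [14] can include a child who stopped the earlier product well before Genotropin. This stands.

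**A stronger reading of the reaction table.** A reader might infer that first-year reactions will look rarer than they are because switched children had already tolerated growth hormone. The documents do not support this. No listed item records tolerance of the earlier product or the reason for switching. A child who switched because of an adverse event could push the other way.

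**Conclusion.** The point holds for HbA1c. The plan pools two groups with potentially different baselines, although it collects the data to separate them and its objective names the factor that divides them. The pooled mean understates the naive change if growth hormone shifts HbA1c and part of that shift came before Genotropin (r below 1). The size is unknown, because s, r, d and the SD are all assumed. At s = 20% the pooled value is 80% to 90% of the naive change for r = 0 to 0.5, and at s = 0 or r = 1 there is no bias.

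For reaction timing, only the lack of separation is established. A reader might conclude that both tables lean towards apparent safety; the documents give no direction for the reaction table. Nor can a split be said to be absent from the whole plan, because SAP 8.2.3.4 is redacted and might contain one. The analysis is exploratory, so no test or decision rule is affected. What is affected is what the reported mean and interval describe.

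**What to change.** **SAP 8.2.3.3.** Keep the pooled summary. Add measured HbA1c and change from start, with 95% confidence interval and number of children, separately for those with and without prior growth hormone. Set the flag from protocol 6.2 item [14] and from whether the date of first growth hormone precedes the Genotropin start date. Item [14] alone covers only growth hormone given for SGA dwarfism, so the date comparison is needed as well.

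**SAP 8.2.3.1.** Show the reaction-timing counts by prior growth hormone yes/no, still on the Genotropin clock, with the number of patients in each group.

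Do not add a table timed from the first growth hormone date. Events before Genotropin are not collected, so previously treated children would contribute early time in which no reaction could be recorded, and the early rows would be falsely low (left truncation).

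**Cost.** SAP wording and extra columns from data already collected. Intervals within each group are wider: with 400 children, s = 20% and the assumed SD of 0.3, the half-width goes from 0.029 pooled to 1.96×0.3/√320 = 0.033 in naive children and 1.96×0.3/√80 = 0.066 in previously treated children. The flag will not separate direct switches from children who had a gap, because the listed items do not include a stop date for the earlier product.
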